4.1. Inclusion Criteria

- Male or female patients, ≥ 18 years of age, able to understand and give written informed consent.
- Histologically or cytologically confirmed epithelial cancer of one of the following types:
 - Gastric adenocarcinoma (GC)
 - Esophageal cancer (EC)
 - Hepatocellular carcinoma (HCC)
 - Non-small-cell lung cancer (NSCLC) CCI [REDACTED]
[REDACTED]
[REDACTED]
[REDACTED]
 - Small-cell lung cancer (SCLC)
 - Epithelial ovarian cancer (EOC)
 - Cervical Cancer
 - Endometrial Cancer
 - Triple-negative breast cancer CCI [REDACTED]
[REDACTED]
[REDACTED]
[REDACTED]
[REDACTED]
[REDACTED]
 - Non-triple-negative breast cancer
 - Papillary thyroid cancer (*excludes follicular, medullary, Hurthle cell, and anaplastic thyroid cancer*)
 - Glioblastoma multiforme (GBM)
 - Hormone-refractory prostate cancer (HRPC)
 - Head and neck cancers- squamous cell (SCCHN)
 - Renal cell cancer (clear cell) (RCC)
 - Urothelial cancer CCI [REDACTED]
[REDACTED]
[REDACTED]

CCI

- Stage IV (metastatic) disease (except for patients with GBM).
- Refractory to or relapsed after at least one prior standard therapeutic regimen.

(Appendix 1 lists approved or standard chemotherapeutic agents for each cancer type. Patients who have not received all approved or standard treatments for their cancer must be informed that these alternatives to receiving IMMU-132 are available prior to consenting to participate in this trial.)

- Adequate performance status (ECOG 0 or 1) ([Appendix 2](#)).
- Expected survival \geq 6 months.
- Measurable disease by CT or MRI.
- At least 2 weeks beyond treatment (chemotherapy, investigational drugs including small molecular inhibitors, endocrine therapy, immunotherapy and/or radiation therapy) or major surgery and recovered from all acute toxicities to Grade 1 or less (except alopecia).
- At least 2 weeks beyond high dose systemic corticosteroids (however, low dose corticosteroids < 20 mg prednisone or equivalent daily are permitted).
- Adequate hematology without ongoing transfusional support (hemoglobin > 9 g/dL, ANC $> 1,500$ per mm 3 , platelets $> 100,000$ per mm 3).
- Adequate renal and hepatic function (creatinine $\leq 2.0 \times$ IULN, bilirubin ≤ 1.5 IULN, AST and ALT $\leq 3.0 \times$ IULN or 5 x IULN if know liver metastases).
- Otherwise, all toxicity at study entry \leq Grade 1 by NCI CTCAE v4.0.

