- Blood samples prior to infusion:
 - CBC (with differential and platelet count)
 - Serum chemistry panel (glucose, creatinine, BUN, total bilirubin, AST, ALT, CCI [REDACTED], alkaline phosphatase, serum albumin, total protein, Na, K, calcium, Cl, CO₂, magnesium and phosphorus)
 - PT/PTT [*required only on Day 1 of all even numbered cycles (cycle 2, 4, 6, 8, etc.)*]
- Urinalysis (*required only on Day 1 of all even numbered cycles starting with cycle 2*)
- Physical examination (*required only on Day 1 of all even numbered cycles starting with cycle 2*)
- 12-lead EKG done [*required after completing infusion on Day 1 of all even numbered cycles (cycle 2, 4, 6, 8, etc.)*]
- Concomitant medications (continued, changed)
- Adverse event reporting
- Serum samples for PK analysis: (frozen, to be shipped to Sponsor for analysis). CCI [REDACTED]
[REDACTED]
[REDACTED]

If samples are not collected with the first dose, then all samples should be obtained with the first dose of a subsequent cycle as advised by the Sponsor.

- HAHA sample (frozen, to be shipped to Sponsor for analysis) **CCI** [REDACTED]
- Pregnancy test, if applicable [*required only on Day 1 of all even numbered cycles (cycle 2, 4, 6, 8, etc.)*]

CT or MRI examinations **CCI**

Starting with the initial dose of IMMU-132, **CT or MRI scans** **CCI** [REDACTED] and are to be obtained at 8 week intervals after the first treatment dose until the occurrence of progression of disease requiring discontinuation of further treatment. For scans showing stable disease, but with substantial or rapid tumor shrinkage near threshold for a partial response, the 8-week interval for the next scan may be shortened at investigator discretion and if discussed with the medical monitor. Confirmatory CT/MRI scans are to be obtained in any patient within 4 to 6 weeks of an initial partial response and/or complete response. If a confirmatory scan is performed, then subsequent scans will be scheduled every 8 weeks from the date of confirmatory scan.

Note: MRI abdomen and pelvis with contrast may be done in situations where a CT with contrast is equivocal or contraindicated. A non-contrast chest CT should be done for patients requiring an MRI of the abdomen and pelvis.

CCI

Additional CT or MRI studies may be performed at the discretion of the physician to assess disease status as medically indicated.

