5.2.1. Demographics

Baseline demographic data summaries will include age, age group, sex, race, ethnicity, height, weight, body mass index (BMI), and number of subjects with renal impairment and hepatic impairment.

Patient demographic data will also be summarized for the subgroups as identified and defined in [Section 6.10](#) and [Section 7.1](#).

Age will be calculated as: Age = Integer \leq [(Informed Consent Date – Date of Birth + 1) / 365.25].

Body mass index will be calculated as: BMI (kg/m²) = weight in kg / (height in m²).

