7.1. Adverse Events

Treatment-emergent adverse events (TEAEs) are defined as any AEs that begin or worsen on or after the start of study drug through 30 days after the last dose of study drug. All AEs will be coded using Medical Dictionary for Regulatory Activities (MedDRA) Version 20.0 unless otherwise specified. The severity will be graded based on the National Cancer Institute's (NCI) Common Terminology Criteria for Adverse Events (CTCAE) Version 4.03. All AEs will be listed. Only TEAEs will be summarized and will be referred to as AEs hereafter. Timing of AEs and concomitant medications will take account of the date and the time of the AE or concomitant medication.

The frequency and severity of AEs will be tabulated by MedDRA SOC and PT. For this purpose, an AE that occurs more than once within each patient will be counted only once (at the worst CTCAE grade and relationship category). Adverse event tables will be sorted by SOC frequency and within each SOC, the PTs will be sorted by decreasing frequency for the total IMMU-132 treated patients' column reported in each table.

Additional by-patient listings will be provided for AEs leading to on-treatment death, serious AEs (SAEs), and AEs leading to discontinuation of treatment (excluding AEs leading to death).

Tables summarizing the incidence of AEs will be generated for each of the following:

1. Overall summary of AEs
2. All AEs by SOC and PT
3. Most common AEs (defined as $\geq 10\%$ of the total number of patients) by PT
4. Grade 3 or higher AEs by SOC and PT
5. AEs by SOC, PT, and grade; columns for: any grades; grade 3, grade 4, grade 5
6. Treatment-related AEs by SOC and PT
7. Treatment-related grade 3 or higher AEs
8. SAEs by SOC and PT
9. Treatment-related SAEs by SOC and PT
10. AEs leading to permanent treatment discontinuation by SOC and PT
11. AEs leading to dose interruption by SOC and PT
12. AEs leading to on-treatment death by SOC and PT, where AEs leading to death is defined as any event of grade 5 and/or outcome equal to fatal, and on-treatment death is defined as date of death within 30 days of last dose

All TEAEs by SOC/PT and the overall TEAE summary table for the following subgroups will be provided when the numbers of patients are deemed sufficient for the Target mTNBC Population and for the Overall Safety Population:

- Age (<50, 50-65, >65 years)
- Sex (male and female) - only for the Overall Safety Population
- Race
- Ethnicity

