- Types of Malignancy according to patient's eligibility criteria CRF - only for the Overall Safety Population
- ECOG Performance Score
- Renal Impairment (creatinine >ULN; creatinine \leq ULN)
- Hepatic Impairment, as defined by baseline serum bilirubin:
 - Normal (\leq ULN)
 - >1 -1.5ULN (> 1 and $\leq 1.5 \times$ ULN)
 - >1.5 ULN ($> 1.5 \times$ ULN)
- UGT1A1 (including but not limited to: *1/*1; *1/*28; *28/*28; not done or missing combined in 1 group)

For the mUC and mBC populations, subgroup analyses of all TEAEs by SOC/PT summary table and the overall TEAE summary table will be done for hepatic impairment and UGT1A1 subgroups, respectively, as defined above.

For the Overall Safety Population, additional subgroup safety analyses including treatment-related AEs and SAEs will be summarized by SOC and PT for hepatic impairment and UGT1A1 subgroups.

In addition to analyses of AEs, adverse events of special interest (AESI) will be assessed. Definitions of AESI, as currently defined, are provided in [Table 6](#), including but not limited to listed. For AESI, frequency tables will be generated, showing overall summary of AESI, Summary of AESI by SOC and PT, Serious AESI by SOC and PT, AESI leading to discontinuation by SOC and PT, AESI leading to treatment interruption by SOC and PT, Grade 3 or higher AESI by SOC and PT, treatment-related AESI (by a worst CTCAE grade of 3, 4, or 5, ≥ 3 and any grade) by SOC and PT. Corresponding listings will also be produced.

Table 6: Definitions of Adverse Events of Special Interest

Adverse event of Special Interest	Definition
Diarrhea	Preferred term: diarrhea
Nausea	Preferred term: nausea
Vomiting	Preferred term: vomiting
Neutropenia+	Preferred terms: neutropenia, neutrophil count decreased, febrile neutropenia
Febrile neutropenia+	Preferred term: febrile neutropenia
Infections	SOC: infections and infestations
Anemia+	Preferred terms: anemia; hemoglobin decreased
Thrombocytopenia+	Preferred terms: thrombocytopenia; platelet count decreased
Fatigue	Preferred term: fatigue and asthenia
Neuropathy+	Preferred term: gait disturbance, hypoesthesia, muscular weakness, neuropathy peripheral, paresthesia, and peripheral sensory neuropathy

Abbreviation: SMQ=Standard MedDRA Query

All definitions based on MedDRA vs 20.0

+ Grouped AE terms

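### Renal impairment is classed by serum creatinine against ULN alone, with no stated time point, so patients with reduced clearance can be tabulated as unimpaired and some with normal clearance as impaired

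*SAP*

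**What the plan says.** SAP Section 7.1 lists the subgroups for the TEAE tables. The renal line reads "Renal Impairment (creatinine >ULN" against creatinine at or below ULN: two groups, with no time point and no clearance or eGFR term. The next line is fuller: "Hepatic Impairment, as defined by baseline serum bilirubin", with three levels.

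These tables "will be provided when the numbers of patients are deemed sufficient for the Target mTNBC Population and for the Overall Safety Population". SAP Sections 5.1, 5.2.1 and 5.5 also refer to the Section 7.1 subgroups for disposition, demographics and exposure.

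SAP Section 5.2.1 separately reports the "number of subjects with renal impairment and hepatic impairment" as a baseline item, alongside age, sex and weight. Apart from Section 7.1 no definition of that count is visible. Section 6.10, to which 5.2.1 also refers, is blacked out.

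Protocol Section 6.3 requires serum creatinine in the pre-treatment chemistries. Eligibility in Protocol Section 4.1 is also set on serum creatinine (up to 2.0 times the institutional ULN). Neither document, as far as it can be read, mentions creatinine clearance or eGFR.

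**The concern.** A renal subgroup is meant to show whether adverse events differ with renal function. The same serum creatinine corresponds to very different clearances in a small elderly woman and a large young man. A cut at ULN therefore sorts patients partly by age, body size and sex.

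Two outputs depend on the label. One is the baseline count of renally impaired patients. The other is the comparison of adverse events between the two groups, where patients with reduced clearance may sit in the reference group. ULN may also differ between sites, because Protocol Section 6 has routine procedures done locally, so one creatinine value could be labelled differently at two sites.

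Since the renal line names no time point, a programmer could also use a value other than baseline.

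**Working it through.** The plan gives no figure to reproduce here, so the check is whether the creatinine split can misplace patients and what that could do to the contrast.

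**Inputs from the documents.** Definition: creatinine above, or at or below, ULN (SAP 7.1). Baseline age, sex and weight (SAP 5.2.1) and creatinine (Protocol 6.3) are available. Population sizes: about 495 (Overall Safety) and 108 (Target mTNBC), both SAP Section 4.

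**Assumptions, not in the documents.** ULN 1.0 to 1.2 mg/dL for the cases in steps 1 and 2, and 1.2 to 1.3 mg/dL for the man in step 3; a reference clearance of 60 mL/min; all ages, weights and creatinine values below; and the event risks and group shares in steps 4 and 5.

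**Formula.** Cockcroft-Gault: CrCl = (140 − age) × weight / (72 × creatinine), times 0.85 for women.

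**1. Reduced clearance, labelled unimpaired when ULN is at or above the value**

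- Woman, 70 y, 55 kg, creatinine 1.0: 70 × 55 / 72 × 0.85 = 45.5 mL/min.
- Woman, 60 y, 60 kg, creatinine 1.1: 80 × 60 / 79.2 × 0.85 = 51.5 mL/min.
- Man, 75 y, 70 kg, creatinine 1.2: 65 × 70 / 86.4 = 52.7 mL/min.

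**2. Age at which a 65 kg woman exactly at ULN falls below 60 mL/min**

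Age > 140 − 60 × 72 × ULN / (65 × 0.85) = 140 − 78.19 × ULN.

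| ULN (mg/dL) | Crossing age | First whole year below 60 |
|---|---|---|
| 1.0 | 61.8 | 62 |
| 1.1 | 54.0 (just under) | 54 |
| 1.2 | 46.2 | 47 |

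**3. The opposite error.** Man, 40 y, 95 kg, creatinine 1.4: 100 × 95 / (72 × 1.4) = 94.2 mL/min. He is labelled impaired at a ULN of 1.2 or 1.3.

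**4. Possible effect on the contrast.** Suppose all patients with reduced clearance share risk r1, the others have risk r0, and a share c of the group at or below ULN has reduced clearance. The observed difference is then (1 − c)(r1 − r0). With r0 = 30% and r1 = 50%, c = 10, 20 or 30% gives 18, 16 or 14 points instead of 20. If risk does not depend on clearance, r1 = r0 and nothing is lost.

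**5. Precision, for scale.** With 10% of patients above ULN and risks of 50% and 30%:

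- N = 495: 1.96 × √(0.25/49.5 + 0.21/445.5) = 14.6 points.
- N = 108: 1.96 × √(0.25/10.8 + 0.21/97.2) = 31.2 points.

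An attenuation of 2 to 6 points is small beside either half-width, especially in the mTNBC set.

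**The case against.** A reader might infer three stronger claims: that the renal comparison is in fact diluted toward no difference, that many women in the mTNBC population are misplaced, and that the impaired count is too low. The documents support none of them. They give no creatinine distribution, no clearance data and no evidence that toxicity depends on renal function. The background in Protocol Section 1 describes hepatic and biliary handling of irinotecan and SN-38. Because misclassification runs both ways, the net error in the count is unknown. The worked patients are hypothetical, and the threshold ages apply only to creatinine exactly at ULN.

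Nor must a clearance cut enlarge the contrast. Take risks of 30% (normal clearance, 70% of patients), 40% (reduced clearance but creatinine at or below ULN, 20%) and 55% (above ULN, 10%, all with reduced clearance).

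- Creatinine split: 55 − (0.7 × 30 + 0.2 × 40)/0.9 = 22.8 points.
- Single cut at 60 mL/min: (0.1 × 55 + 0.2 × 40)/0.3 − 30 = 15.0 points.

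That stands against a single clearance cut and against any claim about direction. It does not defend the creatinine split: under the same assumptions the contrast between normal clearance and above ULN is 25 points, the split shows 22.8, and the intermediate 40% group cannot be seen.

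It is also fair that the tables are descriptive, that the adverse-event tables depend on sufficient numbers, that age is already a separate subgroup ("Age (<50, 50-65, >65 years"), that the split uses the same measure as eligibility, and that SAP 7.1 allows further adverse-event analyses. The popPK plan is a separate document, so its content cannot be counted either way. These points limit the stakes. They do not supply a definition of renal impairment that takes account of age and body size.

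**Conclusion.** The point holds as one about classification. The visible definition can tabulate older or lighter patients with clearances of about 45 to 53 mL/min as unimpaired, and a young, heavy patient at about 94 mL/min as impaired. It also omits the baseline time point that the hepatic line states. These examples rest on the Cockcroft-Gault formula and an assumed ULN of 1.0 to 1.2 mg/dL (1.2 to 1.3 for the young man).

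Attenuation of the adverse-event contrast is possible if risk depends on clearance: 2 to 6 points of a 20-point difference under the assumed shares. Its size and direction in this trial are unknown. The affected outputs are the baseline impairment count and descriptive subgroup summaries. No primary analysis is affected.

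**What to change.** In SAP Sections 5.2.1 and 7.1:

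- Add renal function classes by baseline Cockcroft-Gault clearance: at least 90, 60 to under 90, 30 to under 60, and under 30 mL/min, merging sparse classes.
- Derive them from the baseline creatinine, age, weight and sex already collected.
- State that the baseline value is used, as the hepatic line does.
- Keep creatinine above versus at or below ULN as a supportive split.

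The cost is one derived variable and smaller cells, which matters most in the 108-patient mTNBC population. No new assessment is needed, and eligibility and treatment rules are not involved.

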All patients must have measurable disease by CT or MRI at the time of treatment, but no single lesion \geq 7 cm in diameter. Patients with any bulky lesions over 7 cm, but otherwise eligible, may be considered for enrollment after discussion and approval by the medical monitor (Sponsor). Patients who have not received all approved or standard treatment lines for their cancer must be informed that these alternatives to receiving IMMU-132 are available prior to consenting to participate in this trial. Patients must be 2 weeks beyond any major surgery, radiation, immunotherapy, endocrine therapy, investigational drugs including small molecular inhibitors, or chemotherapy regimens, and have recovered from any acute toxicities associated with these prior treatment(s) to Grade 1 or less (except alopecia).

Patients must have a life expectancy \geq 6 months, an ECOG performance score of 0 or 1, adequate hematology without ongoing transfusional support (ANC \geq 1.5 x 10⁹/L, platelets \geq 100 x 10⁹/L, hemoglobin $>$ 9 g/dL), no active \geq Grade 2 anorexia, nausea or vomiting or signs of intestinal obstruction, no prior history of clinically significant bleeding, intestinal obstruction, or GI perforation within 6 months, no known history of anaphylactic reaction or \geq Grade 3 GI toxicity to prior irinotecan, no known history of unstable angina, MI, or CHF present within 6 months or clinically significant cardiac arrhythmia (other than stable atrial fibrillation) requiring anti-arrhythmia therapy, no known history of clinically significant, active COPD, or other moderate to severe chronic respiratory illness present within 6 months, adequate renal (creatinine \leq 2.0 x IULN) and hepatic function (bilirubin \leq 1.5 x IULN, AST and ALT \leq 3 x IULN or 5 x IULN if known liver metastases), and with otherwise all toxicity at study entry $<$ Grade 1 by NCI CTC v4.0 (Patients with \leq Grade 2 neuropathy will be eligible). Patients with Gilbert's disease are excluded. Patients with treated, non-progressive brain metastases, off high-dose steroids (>20 mg prednisone or equivalent) for at least 4 weeks, can be enrolled in the trial.

Patients with successfully treated non-melanoma skin cancer or carcinoma in situ of the cervix are eligible, while patients with other prior malignancies must have had at least a 3-year disease-free interval.

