SN-38, a topoisomerase I inhibitor, is the active metabolite of the camptothecin CPT-11 (irinotecan), which is approved as a single agent for colorectal cancer and included in treatment regimens such as FOLFIRI.⁽¹²⁻²⁰⁾ SN-38 is not water soluble, and therefore it was derivatized to a water-soluble form, irinotecan, but it must be enzymatically cleaved to the SN-38 form for it to have maximum potency. Unfortunately, at best, only 5% of irinotecan will be converted to the active SN-38 form by esterase activity residing primarily in the liver, albeit there are esterases in the tumor that can cleave irinotecan to SN-38.⁽²¹⁻²⁴⁾ Its catabolism in the liver results in its transport through the bile duct into the intestines, resulting in GI toxicity.

[figure not shown]
CCI

A large block of text has been redacted with black bars. The word 'CCI' is printed in red at the top of this redacted area.

CCI

Immunomedics is currently pursuing several ADCs based on the SN-38 conjugation technology it developed. In this protocol, a humanized anti-Trop-2 antibody (hRS7) is examined. Trop-2 (trophoblastic cell-surface antigen; also known as EGP-1, epithelial glycoprotein-1), is a cell surface, transmembrane calcium signal transducer glycoprotein belonging to the TACSTD gene family that is highly expressed in many epithelial cancers, particularly metastatic sites⁽²⁷⁾, with much lower expression in normal tissues.⁽²⁸⁾ Trop-2 has been implicated as an important antigen in oncogenesis, often being found in more aggressive tumors⁽²⁹⁻³⁹⁾. The murine RS7 antibody was initially identified as being specific for epithelial glycoprotein-1 (aka, Trop-2)^(40, 41), being found in a number of different epithelial cancers and it was internalized⁽⁴²⁻⁴⁵⁾, a highly desirable property for an antibody-drug conjugate. Indeed, as mentioned above, the initial studies with the SN-38 conjugates used an anti-CEACAM5 antibody that is not readily internalized, yet it was potent *in vivo*, leaving us to hypothesize that local release of the SN-38 from the antibody bound to the tumor provides an important mechanism for that conjugate's activity. However, the hRS7-SN-38 conjugate further benefits from the antibody's ability to internalize.⁽⁴⁶⁾

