7.3. Clinical Laboratory Evaluations

Clinical laboratory data results will be reported in standard international units and US conventional units. Baseline is defined as the last observation occurring prior to the first treatment administration of IMMU-132. Observations occurring on the same day as first

[figure not shown]
treatment day will be the baseline assessment as they are assumed to have occurred prior to the time of treatment according to study schedule.

If a lab value is reported using a non-numeric qualifier (eg, less than [$<$] a certain value, or greater than [$>$] a certain value), the given numeric value will be used in the summary statistics, ignoring the non-numeric qualifier.

Hematology and serum chemistry data will be listed by patient and summarized by study visit. Actual values by visit and change-from-baseline will be summarized by mean, median, standard deviation, minimum, maximum and number of patients.

Shift tables from baseline to worst CTCAE grade on treatment and from worst to last CTCAE grade on treatment will be presented where CTCAE grade is available. Shift tables will be presented based on CTCAE v4.03 criteria, using the grades 1 through 4 as well as a grade 0 indicating no abnormality. These shift tables will report the shift from baseline CTCAE grade to worst grade on treatment and from worst to last on-treatment visit.

For liver function tests, summaries of maximum alanine aminotransferase (ALT), maximum aspartate aminotransferase (AST), and maximum total bilirubin level (TBL) will be produced to evaluate for possible drug-induced liver injury (DILI), including presentation of Hy's law/evaluation of drug-induced serious hepatotoxicity (eDISH) figures (see figure below). For the eDISH figures the horizontal and vertical lines for 2ULN and 3ULN will be selected based on the lowest available reference range for each parameter. In addition, tables will be produced summarizing the number and percentage of patients with multiples of the upper limit of normal (ULN) for AST and ALT (≤ 3 ULN, >3 ULN) and bilirubin (≤ 2 ULN and >2 ULN) and for patients who fulfil either AST or ALT >3 ULN in conjunction with bilirubin >2 ULN.

Patients with elevated ALT or AST ($>3 \times$ ULN) or bilirubin ($>2 \times$ ULN) will be flagged on the relevant listing of laboratory data.

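### The hepatic-impairment safety subgroup uses baseline bilirubin alone, so eligible patients with raised AST or ALT count as Normal and the contrast may be attenuated

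*SAP*

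**What the plan says.** SAP 7.1 lists the subgroups for the adverse-event tables. One is "Hepatic Impairment, as defined by baseline serum bilirubin", with three categories: Normal (at or below ULN), above 1 and up to 1.5 times ULN, and above 1.5 times ULN. AST and ALT play no part. The subgroup serves the tables of all treatment-emergent events and, in the Overall Safety Population (about 495 patients), also treatment-related events and serious events. SAP 5.2.1 adds a baseline summary of the "number of subjects with renal impairment and hepatic impairment" and gives no definition of its own.

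Protocol 4.1 and the synopsis set the entry limits. AST and ALT may reach 3 times the institutional limit, or "5 x IULN if known liver metastases". Bilirubin is held tighter: "bilirubin ≤ 1.5 IULN".

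AST and ALT are analysed in SAP 7.3 as laboratory outcomes, through values by visit, shift tables, plots for drug-induced liver injury, and "summaries of maximum alanine aminotransferase (ALT), maximum aspartate aminotransferase (AST), and maximum total bilirubin level (TBL) will be produced". No adverse-event table is split by baseline AST or ALT.

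**The concern.** The entry rules allow more room for abnormal transaminases than for abnormal bilirubin, but the subgroup sorts patients on bilirubin only. A patient with liver metastases, AST at 5 times the limit and normal bilirubin is eligible and is tabulated as Normal under a heading of hepatic impairment. All patients except those with glioblastoma have Stage IV disease, and the Protocol expressly provides for liver metastases, so such patients are to be expected.

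The Protocol treats the liver as relevant to toxicity. Protocol 4.3 warns that effects on liver metabolism of irinotecan and SN-38 may alter the toxicity profile. The Introduction, in its account of irinotecan and SN-38, says: "Its catabolism in the liver results in its transport through the bile duct into the intestines, resulting in GI toxicity". The hepatic tables are where a reader would look for a difference in tolerability. If patients with abnormal liver tests carry extra risk and sit in the reference category, the displayed difference is smaller than the one between patients with normal liver tests and those with raised bilirubin. The baseline count of hepatic impairment would also be too low.

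**Working it through.** **Step 1. Classification, from the text alone.** No assumption is needed here.

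| Baseline finding | Allowed at entry? | SAP 7.1 category |
|---|---|---|
| Bilirubin, AST and ALT all ≤ ULN | Yes | Normal |
| Bilirubin ≤ ULN, AST or ALT > ULN up to 3 × (5 × with known liver metastases) | Yes | Normal |
| Bilirubin > 1 to 1.5 × ULN | Yes | > 1 to 1.5 × ULN |
| Bilirubin > 1.5 × ULN | Not at screening | > 1.5 × ULN |

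Because of the bilirubin cap, the last category should hold few eligible patients. The usable contrast is mainly the first category against the second.

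**Step 2. Size of the attenuation.** The SAP states no figure for this subgroup, so there is nothing to reproduce. Let

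- r0 = event risk with all three liver tests normal,
- r1 = event risk with raised bilirubin,
- f = share of the Normal category with AST or ALT > ULN,
- k = share of the excess risk r1 − r0 carried by isolated AST or ALT elevation.

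The risk shown for Normal is (1 − f)·r0 + f·[r0 + k(r1 − r0)] = r0 + f·k·(r1 − r0).

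The difference shown is r1 minus this, that is (r1 − r0)(1 − f·k). The relative attenuation is f·k, whatever r0 and r1 are. All values of f and k below are assumed.

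| f | k = 0 | k = 0.5 | k = 1 |
|---|---|---|---|
| 0.05 | 0% | 2.5% | 5% |
| 0.10 | 0% | 5% | 10% |
| 0.20 | 0% | 10% | 20% |
| 0.30 | 0% | 15% | 30% |
| 0.40 | 0% | 20% | 40% |

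Example with assumed r0 = 0.30 and r1 = 0.45. At f = 0.20 and k = 1 the Normal category shows 0.33 and the difference is 0.12 instead of 0.15. At f = 0.40 and k = 1 it shows 0.36 and the difference is 0.09.

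**Step 3. Would pooling isolated AST or ALT elevation with mildly raised bilirubin be better?** Let a be the share of all patients with isolated elevation and b the share with raised bilirubin, so f = a/(1 − b). The current rule keeps the fraction 1 − f·k of the contrast. A pooled category, set against a cleaned Normal, keeps (a·k + b)/(a + b). With assumed b = 0.05:

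| a | f | k | Current rule keeps | Pooled category keeps |
|---|---|---|---|---|
| 0.20 | 0.211 | 0 | 100% | 20% |
| 0.20 | 0.211 | 0.5 | 89% | 60% |
| 0.20 | 0.211 | 1 | 79% | 100% |
| 0.30 | 0.316 | 0 | 100% | 14% |
| 0.30 | 0.316 | 0.5 | 84% | 57% |
| 0.30 | 0.316 | 1 | 68% | 100% |

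The two are equal at k = (1 − b)/(1 + a): 0.95/1.20 = 0.79 and 0.95/1.30 = 0.73. Below that, pooling hides more than the current rule does. Separate categories keep the full difference r1 − r0 at any k.

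**The case against.** The SAP discloses its rule: the subgroup is stated to rest on bilirubin, and Normal can be read as normal bilirubin. AST and ALT are reported at length in SAP 7.3, and SAP 7.1 leaves room for further adverse-event analyses if warranted. SAP 6.10, which SAP 5.2.1 cites with 7.1 for subgroup definitions, is redacted and may say more. The tables are descriptive, in a single-arm study, and no decision rule hangs on them. All of this stands and limits the weight of the point. It does not cure it: laboratory shift tables do not sort adverse events by baseline AST or ALT, and an optional analysis is not a planned one.

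Three stronger readings are tempting, and the documents do not support them.

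- *The comparison is diluted.* This needs both a material number of such patients and an excess risk from isolated AST or ALT elevation. The documents give neither, and at k = 0 there is no dilution.
- *The category above 1.5 times ULN can contain only eligibility violations.* Screening may precede treatment by up to 4 weeks, chemistries are repeated on Cycle 1 Day 1, and SAP 7.3 takes the last value before dosing as baseline. Bilirubin may rise in between without any violation.
- *All four safety populations are affected.* For the urothelial and non-triple-negative breast populations, SAP 7.1 names the hepatic and UGT1A1 subgroups with the word respectively, which may assign one to each. The tables for the target triple-negative and Overall Safety populations are conditional on sufficient numbers.

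The objection that a broader impaired group could itself shrink the contrast is also right, as Step 3 shows. It bears on the form of the fix.

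**Conclusion.** The point holds as a matter of definition. SAP 7.1 places eligible patients with raised AST or ALT and normal bilirubin in the Normal category, and on the visible text SAP 5.2.1 would not count them as hepatically impaired. The effect on the displayed contrast is possible, not established: 0% to 40% over f from 0.05 to 0.40 and k from 0 to 1, all assumed. Values of k above 1 were not tried. No test, power figure or stated result changes. A reader might extend the criticism to the renal subgroup, which is cut at creatinine above ULN. The documents give no basis for sizing a defect there, and entry up to 2.0 times the institutional limit lets eligible patients fall on both sides of that cut. The hepatic change is worth making because it gives a clean reference category whatever the true k, from data already collected.

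**What to change.** In SAP 7.1, define the hepatic subgroup by four separate categories:

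1. Normal: bilirubin, AST and ALT all at or below ULN.
2. Bilirubin at or below ULN with AST or ALT above ULN.
3. Bilirubin above 1 and up to 1.5 times ULN.
4. Bilirubin above 1.5 times ULN.

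A pooled mild category (2 with 3) may be added but should not replace the separate ones. Use the same definition for the count in SAP 5.2.1.

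The cost is a change of SAP wording, one derived variable from the required baseline chemistry panel, one more table column, and a smaller reference category.
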